### **Statistical Analysis:**

#### **Definitions of the statistics of interest:**

Let A+ denote the event that the test is positive for hematoma and B+ denote the event that a hematoma is present. Sensitivity,  $P(A+/B+)$ , will be defined for each patient (scan) as the probability that a true hematoma as determined by CT scan will be detected (14). Similarly, let A- denote the event that the test is negative for hematoma and B- denote the event that a hematoma is not present. Specificity,  $P(A-/B-)$ , will be defined as the probability of being negative for hematoma on the InfraScanner 2000™ scan within 30 minutes of CT given the patient has no hematoma present.

The false positive rate will be defined as  $PF+ = P(B-/A+) = P(A+/B-)[1-P(B+)]/P(A+)$ . Similarly, the false negative rate will be defined as  $PF- = P(B+/A-) = [1-P(A+/B+)]P(B+)/[1-P(A+)]$ . Estimates for the false positive and false negative rates will be provided for a range of values for the prevalence of hematomas.

1. Estimation of test characteristics with 90% confidence at the patient level using SAS 9.4;
2. Estimate test characteristics at the scan level (treat each measurement as independent sample) and 95% confidence intervals will be computed as a secondary analysis.
3. Estimating Receiver Operating Characteristic (ROC) curves with patient and scan as the units of analysis with 95% confidence interval.
4. Fit a logistics regression of correct and incorrect detection from InfraScanner, adjusting for age, gender, skin color, hair color, hair thickness, hair length, scalp hematoma, scalp laceration, scalp fracture, ventricular effacement and midline shift.

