procedure will be explained in detail, using an IRB-approved verbal consent “script”, with all questions answered to the patient’s and/or representative’s satisfaction. Because patients who sustain head trauma injuries typically remain within the hospital for multiple days for monitoring and care, each participant may undergo multiple CT scans over the course of his or her hospitalization, affording the opportunity to one to numerous measurements from each patient during his or her hospital stay. When subjects are approached for subsequent study measurements, if the subject has regained the capacity to consent or has an LAR present, the verbal script will be used to obtain consent. Subjects will be asked at that time if prior measurements obtained may be used in the research.

Within 30 minutes following each CT scan, the study team will approach the patient to scan the patient’s cranium with the InfraScanner 2000™ (Image A). The procedure will entail placing 8 plastic light guides upon the patient’s scalp. The study team member will use the device to sequentially emit light through each of the 8 light guides so that the light is incident upon scalp (Image B). The device is engineered such that the light emitter and receiver are spaced ~4cm apart, allowing the light’s intensity to be measured between adjacent light guides (Image C). This entire procedure, including greeting the patient, placing the light guides, gathering the data, and removing the light guides should take ~10 minutes each time. The number of CT scans the patient receives determines the number of potential data collections. The patient will be approached by the study team following each CT scan to be scanned with the InfraScanner 2000™ (20). The patient and/or representative may refuse a scan during any encounter, and as such, the scan will not be done. For each patient scanned with the InfraScanner 2000™ they will be de-identified with a subject number, with age, sex, gender, skin color, hair color, hair thickness, mechanism of injury, Glasgow Coma Scale score, and mean time elapsed between CT scan and near-infrared measurement. These data will be stored in de-identified form on Research Electronic Data Capture (REDCap), Duke Box, and/or Microsoft Excel 2016 on a secured DHTS server (S:\NSU_IRB\Pro00087011).

The collection period for each research subject concludes 30-days following his or her initial measurement with the InfraScanner 2000™, patient discharge, or patient death.

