- 13. Statistical Considerations:** Objectives: The primary objective of this study is to estimate the test characteristics (sensitivity, specificity, and the false positive and false negative rates) of the portable NIR-based device (InfraScanner 2000™) in the identification of any size hematoma among patients hospitalized at DUH who have sustained or who are suspected to have sustained head trauma and have consequently received a brain CT scan(s). The results of the CT scan(s) will serve as the gold standard. The sensitivity, specificity, and the false positive and

false negative rates will be estimated at the patient level and at the scan level. Approximately 90% of patients are expected to have more than one CT scan.

A secondary objective is to estimate the test characteristics of the InfraScanner 2000™ in identification of hematomas within its detection limits (volume >3.5 mL and depth <2.5 cm) compared to CT scan results as the gold standard.

Exploratory objectives include:

1. Examining the impact of factors such as hematoma type, location, and patient age on test characteristics of the InfraScanner 2000™
2. Determining the minimum resolution detectable by the InfraScanner 2000™
3. Estimating Receiver Operating Characteristic (ROC) curves with patient and scan as the units of analysis (21).

Study Design:

a) Eligibility:

Any patient who presents to DUH with suspected head trauma and receives a brain CT scan will be considered for this study. Based on previously reported data, we expect that SDH or EDH will be present in approximately 20% of patients overall.

b) Standard of comparison:

All patients entered onto the trial will undergo at least one cranial scanning using the InfraScanner 2000™ within 30 minutes of CT. Patients will be scanned using the InfraScanner 2000™ within 30 minutes of each subsequent CT. Patients will know the results of the CT but not the InfraScanner 2000™. The standard for comparison will be determined as follows. A CT result that is positive for hematoma will be considered a true positive and a CT result that is negative for hematoma will be considered a true negative. In cases where the results of the CT are negative for hematoma and the results of the InfraScanner 2000™ are positive consideration of further follow-up will be given on a case-by-case basis.

Definitions of Sensitivity, Specificity, False Positive, False Negative

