Let A^+ denote the event that the test is positive for hematoma and B^+ denote the event that a hematoma is present. Sensitivity, $P(A^+/B^+)$, will be defined for each patient (scan) as the probability that a true hematoma as determined by CT scan will be detected (22). Similarly, let A^- denote the event that the test is negative for hematoma and B^- denote the event that a hematoma is not present. Specificity, $P(A^-/B^-)$, will be defined as the probability of being negative for hematoma on the InfraScanner 2000™ scan within 30 minutes of CT given the patient has no hematoma present.

The false positive rate will be defined as $P_{F+} = P(B^-/A^+) = P(A^+/B^-)[1 - P(B^+)]/P(A^+)$. Similarly, the false negative rate will be defined as $P_{F-} = P(B^+/A^-) = [1 - P(A^+/B^+)]P(B^+)/[1 - P(A^+)]$. Estimates for the false positive and false negative rates will be provided for a range of values for the prevalence of hematomas.

c) Sample Size

Computation of the required number of patients is based on estimating the sensitivity of each method to within at most ± 0.10 with 90% confidence. The 90% confidence interval for the sensitivity is given by $P_{Sens} \pm 1.645 * SE(P_{Sens})$ where $SE(P_{Sens}) = \sqrt{(P_{Sens})(1 - P_{Sens})/N}$; N denotes the number of true positives.

Administrative Summary: Based on an interim analysis conducted after 200 patients were studied, the proportion of patients with hematomas is 0.13. This is lower than the 20% originally expected. The sample size computation was thus revised as follows.

Original sample size computation

With 68 patients with positive findings of hematoma, sensitivity can be estimated to within at most ± 0.099 with 90% confidence. Assuming 20% of patients have true hematomas detected, 340 patients must be accrued (10). Allowing for a 5% dropout rate the required sample size for this trial is 360 subjects. With 272 patients having negative findings for hematoma, specificity can be estimated to within at most ± 0.05 with 90% confidence.

Revised sample size computation

With 68 patients with positive findings of hematoma, sensitivity can be estimated to within at most ± 0.099 with 90% confidence. Assuming 13% of patients have true hematomas detected, 523 patients must be enrolled to observe positive findings in 68 patients. With 455 patients having negative findings for hematoma, specificity can be estimated to within at most ± 0.038 with 90% confidence.

d) Interim Analysis

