**Study Population:**

- Any patient who presents to DUH with suspected head trauma and receives a brain CT scan will be considered for this study. Our final sample size is 581 measurements for 500 patients.

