#### **Analysis plan:**

1. A baseline table (Table 1) will describe overall study cohort characteristics by hematoma status.
2. Hematoma characteristics will be summarized at the patient level and also at the scan level (Table 2 and Table 3).
3. A 2x2 table of CT and InfraScanner results. Sensitivity, specificity, false positive value, false negative value, and their 95% confidence intervals will be calculated at patient level using the contingency table and reported. Repeat the analysis at scan level.
4. 2x2 tables of CT and InfraScanner results by quadrant. Corresponding counts and test characteristics will be calculated for each quadrant (frontal, temporal, parietal, and occipital). Repeat the analysis at scan level.
5. 2x2 tables of CT and InfraScanner results for hematomas within the detection limit. Corresponding counts and test characteristics will be calculated for hematomas within the detection limit (blood volume > 3.5 cc and distance from cranium < 2.5 cm). Repeat the analysis at scan level.

6. 2x2 tables of CT and InfraScanner results by types of hematoma. Corresponding counts and test characteristics will be calculated for each type of hematoma (SDH, EDH, etc.). Repeat the analysis at scan level.
7. 2x2 tables of CT and InfraScanner results by types of hematoma for those within the detection limit. Corresponding counts and test characteristics will be calculated for each type of hematoma (SDH, EDH, etc.) for those within the detection limit (blood volume > 3.5 cc and distance from cranium < 2.5 cm). Repeat the analysis at scan level.
8. Minimum blood volume detected as positive by InfraScanner 2000 will be reported.
9. Distributions of Blood Volumes and Difference in Optical Density ( $\Delta OD$ ) will be plotted for patients with hematoma.
10. InfraScanner results for special cases will be reported. Special cases include: patients who died, or had surgeries (craniectomy or craniotomy), or had ventricular effacement or midline shift.
11. Logistic regression model will be fit to assess the association between InfraScanner result and potential confounders that include patient age, sex, hair length, hair thickness, hair color, skin color, scalp laceration, scalp fracture, and scalp hematoma. Odds ratios with 95% CI will be reported.

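### Scan-level 95% intervals treat 581 measurements on 500 patients as independent and will be too narrow if repeat scans are positively correlated within patient

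*SAP*

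**What the plan says.** - **SAP, Definitions of the statistics of interest, item 2.** The instruction is "Estimate test characteristics at the scan level (treat each measurement as independent sample"), and "95% confidence intervals will be computed as a secondary analysis".
- **SAP, Study Population.** "Our final sample size is 581 measurements for 500 patients".
- **SAP, Definitions of the statistics of interest, item 3.** The plan adds ROC "curves with patient and scan as the units of analysis with 95% confidence interval". It names no variance method for the scan-level curve.
- **SAP, Analysis plan, item 3.** For the overall 2x2 table, "95% confidence intervals will be calculated at patient level using the contingency table and reported. Repeat the analysis at scan level". Items 4 to 7 repeat the tables by quadrant, detection limit and hematoma type at scan level, without saying whether intervals will be given.
- **Protocol section 4, Design and Procedures.** The repeats come from the same people: "each participant may undergo multiple CT scans over the course of his or her hospitalization", and the device is to be used after each one.
- **Protocol section 13, Objectives.** Under the primary objective, sensitivity, specificity and the false positive and "false negative rates will be estimated at the patient level and at the scan level".

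The SAP's Data Management section reduces multiple scans to one result per patient, but only for the patient-level analysis. Neither document mentions a cluster-robust variance, GEE, a mixed model or a cluster bootstrap.

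**The concern.** Two scans of one patient within a 30-day window share nearly the same scalp, hair and skin, and often the same bleed, although a bleed may evolve or resolve. The SAP itself treats skin color, hair color, thickness and length, and scalp injury as possible influences on the device result, since it enters them in its logistic regressions. If those features affect whether the device is right, two results from one patient with the same CT status are not independent.

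An interval that counts every scan as a new patient then claims more information than the data hold. Given positive correlation, the error has one direction: the interval is too narrow. The scan-level intervals for the overall 2x2 table are affected directly. The scan-level ROC interval is affected if the same assumption is carried over to it. The tables in Analysis plan items 4 to 7 are affected only if intervals are reported for them.

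Sensitivity has most at stake. It has the smaller denominator, and it would suffer most if patients with a bleed are re-imaged more often, which is plausible but not stated.

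**Working it through.** **Inputs from the documents**
- 581 measurements and 500 patients (SAP, Study Population), so 581 - 500 = 81 repeats and 581/500 = 1.162 scans per patient.
- Prevalence: at the interim analysis "the proportion of patients with hematomas is 0.13" (Protocol section 13, Sample Size), so 0.13 x 500 = 65 CT-positive and 435 CT-negative patients.
- Sensitivity 0.88 and specificity 0.91, from the pivotal study of the earlier device (SAP, Background). The 0.88 is for hematomas within the detection limits. These two values set the illustrative half-widths only; the percentage widening does not depend on them.

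**Assumptions, because the documents are silent**
- Within-patient correlation (rho) 0.3 to 0.7, with 0.1 as a low case.
- All repeats of CT-positive patients are also CT-positive.
- Three splits of the 81 repeats: 11 in CT-positive patients (0.13 x 81 = 10.5), 40 (about half), or all 81.

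**The plan's own figures.** The documents state no scan-level width. Their patient-level precision reproduces with 1.645 x sqrt(0.25/N): N = 68 gives 0.0997 (stated 0.099) and N = 455 gives 0.0386 (stated 0.038). These count patients and are not in question here.

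**Formulas**, with m the number of scans per patient and n = sum m:
- Design effect DE = 1 + rho x (sum m² / sum m - 1)
- Widening = sqrt(DE)
- Half-width = 1.96 x sqrt(p(1-p)/n) x sqrt(DE)
- Approximate coverage of the planned interval = 2 x Phi(1.96/sqrt(DE)) - 1

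**Worked example, proportional split.** 54 patients with one scan and 11 with two: n = 54 + 22 = 76 and sum m² = 54 + 44 = 98, so 98/76 - 1 = 0.289. At rho 0.3, DE = 1 + 0.3 x 0.289 = 1.087 and sqrt(DE) = 1.042. At rho 0.7, DE = 1.203 and sqrt(DE) = 1.097. The half-width under independence is 1.96 x sqrt(0.88 x 0.12/76) = 0.073; it becomes 0.076 to 0.080.

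| Denominator | Scans per patient | n | DE, rho 0.3-0.7 | Wider by | Half-width: planned, corrected | Approximate coverage as planned |
|---|---|---|---|---|---|---|
| Sensitivity, proportional | 54x1, 11x2 | 76 | 1.087-1.203 | 4-10% | ±0.073, ±0.076-0.080 | 0.94-0.93 |
| Sensitivity, about half | 25x1, 40x2 | 105 | 1.229-1.533 | 11-24% | ±0.062, ±0.069-0.077 | 0.92-0.89 |
| Sensitivity, all repeats | 49x2, 16x3 | 146 | 1.399-1.930 | 18-39% | ±0.053, ±0.062-0.073 | 0.90-0.84 |
| Specificity, proportional | 365x1, 70x2 | 505 | 1.083-1.194 | 4-9% | ±0.025, ±0.026-0.027 | 0.94-0.93 |

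**Sensitivity to the assumptions**
- At rho 0.1 the three sensitivity figures fall to 1.4%, 3.7% and 6.4%.
- The proportional split allows at most one repeat per patient. If the same 11 repeats fall on 4 patients (61x1, 3x4, 1x3), DE is 1.166-1.387 and the interval is 8-18% wider.
- If more repeats fall in CT-positive patients, fewer are left to affect specificity. With all 81 there, the specificity interval is unaffected.

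**Simulation check** (beta-binomial, 65 CT-positive patients, sensitivity 0.88, rho 0.3 to 0.7). A Wilson interval that assumes independence covers 0.94-0.93 (proportional), 0.92-0.88 (half) and 0.92-0.86 (all). A cluster-robust t interval on the linear scale covers 0.94-0.93, and a logit-scale GEE interval about 0.95.

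**The case against.** The scan-level analysis is labelled secondary and its assumption is stated openly. The patient-level analysis is protected because each patient is reduced to one result, and the planned precision targets count patients. The study is an estimation pilot: no threshold, test or go/no-go rule is tied to a scan-level limit. In the one split that assumes no concentration of repeats, the correction is about 0.003 to 0.007 on a half-width of 0.073. The larger figures need half or all of the repeats in CT-positive patients, which the documents do not say. The correlation range has no source, and a repeat whose CT status has changed moves to the other denominator and adds no clustering there. The ROC work is exploratory in the protocol, and the independence instruction is not written into that item.

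Much of this stands. It limits the importance of the point, makes the ROC part an inference, and means the size can only be a range. It does not make the assumption sound. The protocol places scan-level estimation under the primary objective alongside patient-level estimation. The small-effect case cannot be presumed while the split of repeats is unreported. The correction needs no new data.

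**Conclusion.** The concern holds. A written instruction gives scan-level 95% intervals that are too narrow whenever repeat results of the same CT status are positively correlated within patient, and the documents' own list of influences on the device makes that likely.

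The effect is modest if repeats follow prevalence and becomes material for sensitivity if they concentrate in CT-positive patients. At correlation 0.1 it is small in the proportional case and at most about 6% even in the extreme one. All figures rest on the assumed correlation, the assumed split and 65 CT-positive patients; the extreme split is a bound, not an expectation. The SAP's false positive and false negative rates condition on the device result, so they have other denominators and were not quantified.

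The change should be made, but no patient-level conclusion depends on it.

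**What to change.** 1. In the SAP, Definitions of the statistics of interest, item 2, delete the instruction to treat measurements as independent and state that scan-level intervals use patient as the cluster.
2. Prefer SAS PROC GENMOD with a logit link, REPEATED SUBJECT=patient / TYPE=IND and robust standard errors, with limits back-transformed from the logit scale. The independence working correlation leaves point estimates unchanged. PROC SURVEYFREQ with CLUSTER patient is an alternative, but its default linear-scale interval is expected to cover about 0.93-0.94 here.
3. For the scan-level ROC curve and its area, use a patient-level bootstrap that resamples patients with all their scans.
4. Where a sparse table gives 0% or 100% and the robust variance collapses, report an exact or Wilson interval based on the number of patients.
5. Report scans per patient by CT status, so that readers can see how much clustering there is.

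The cost is one SAP sentence, a few lines of SAS and one descriptive row. The scan-level intervals become somewhat wider.

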In Uganda, there are currently 33 ICU beds, 6 government neurosurgeons, and 1 formally trained neurologist to serve, not accounting for the significant international referrals received from neighboring countries, the entire population of 41 million people (18, 19). Despite the profound dearth of care and exceptionally high mortality, Africans pay significantly more out of pocket for medical care than the world (83% versus 26%), which in the case of current TBI care, often leads to incurrence of significant familial hardship for improbable survival (14). This constellation of unmatched mortality, resource famine, and debt incurrence fashion SSA, and MRRH in particular, the ideal setting to pilot a minimal-resource, guideline-driven ICU system. The InfraScanner 2000™ can potentially server as the centerpiece of such a system providing zero-cost, immediately-available, sequential intracranial imaging to help make urgent surgical and medical decisions that can save an untold number of lives that are currently being forfeited due to lack of imaging.

To work toward this, this study proposes compare the sensitivity, specificity, accuracy, and precision of the InfraScanner 2000™ against brain CT scans at DUH. If capable detecting Intracranial hematomas with efficacy similar to CT, expanding the use of the such a device as a CT-substitute to detect intracranial hematomas in places devoid of CT facilities could revolutionize TBI care in LMICs.

4. **Design and Procedures:** When applicable (conscious patient and/or family or legally authorized representative is present) the study will be introduced to the patient and relevant parties prior to the research team approaching the patient. While head trauma frequently results in impaired cognition and/or consciousness, and due to the urgency of these circumstances patients are often not accompanied by kin, whenever appropriate, the purpose of the research and the

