### **Background:**

Traumatic brain injury (TBI) is a global pandemic that affects over 10 million people annually, with the incidence expected to continue to mushroom in coming years (1). In industrialized nations, this is a trivial requirement, as CT scans are used ubiquitously to definitively diagnose epidural hematomas (EPH) and subdural hematomas (SDH), readily and reliably triaging patients to surgical versus medical management. In less developed countries, CT scanners are often nonexistent. When they are present, they are extremely meager in number, peppered across treacherous geography, with scant transportation and emergency infrastructure.

In 1997, the first ever handheld device that could definitively detect the presence and location of epidural and subdural hematomas was introduced (2). Initially named the Runman, the device was intended to detect intracranial hematomas in remote and military settings to triage which casualties should be airlifted to medical centers equipped to offer neurosurgery. After numerous iterations, the InfraScanner 1000™ was introduced in the mid 2000's. In 2010, the pivotal five-site double-blinded clinical trial was published, and ultimately led to FDA clearance of the InfraScanner 1000™. In the study, the Infrascanner 1000™ measurements were compared to CT scans of 365 patients, 96 of which were hematoma cases of various sizes, depths and locations. The study demonstrated high sensitivity (88%) in detecting hematomas > 3.5cc in volume and < 2.5 cm from the surface of the brain, and a specificity of 91%. Since then there have been numerous studies that have replicated these results and have substantiated that it is a capable tool for pre-hospital diagnosis of intracranial hematomas (2-12).

The goal of this study is to determine the sensitivity, specificity, and positive and negative predictive values of the portable near-infrared-based device (portable NIR-based device), the InfraScanner 2000™, to detect intracranial hematomas [EDH and/or SDH] in patients hospitalized at Duke University Hospital (DUH) who have sustained or who are suspected to have sustained head trauma and have consequently received a brain computed tomography (CT) scan(s).

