**Data Management:**

**Explain multiple measurements for the same patients,  
Sample size**

If there are multiple scans on a single patient, define the presence of a hematoma per patient as the first hematoma detected by the Infrascanner on any assessment and compare results with the corresponding CT assessment (within 30 minutes on same date).

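### The SAP's two logistic models pool CT-positive and CT-negative patients, so they greatly understate a factor's effect on sensitivity, and no planned analysis gives sensitivity or specificity by age

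*SAP*

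**What the plan says.** The protocol's first exploratory objective (section 13) is "Examining the impact of factors such as hematoma type, location, and patient age on test characteristics of the InfraScanner 2000™". The SAP defines sensitivity among patients with a CT hematoma, as "the probability that a true hematoma as determined by CT scan will be detected", and specificity among patients without one.

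Two regressions bear on patient factors:

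- **Statistical Analysis, item 4:** "Fit a logistics regression of correct and incorrect detection from InfraScanner". The covariates are age, sex, skin and hair features, three scalp findings, ventricular effacement and midline shift.
- **Analysis plan, item 11:** "Logistic regression model will be fit to assess the association between InfraScanner result and potential confounders". The covariates are the same except that effacement and midline shift are left out. Those two appear instead under item 10, where "InfraScanner results for special cases will be reported".

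Neither item names an analysis set, a CT term or an interaction with CT status, and neither says whether the unit is the patient or the scan. CT positivity is a collected variable (SAP, Variables, item 11). The 2x2 tables in the Analysis plan cover quadrant, detection limit and hematoma type, but not age, sex, skin, hair or scalp findings.

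**The concern.** Sensitivity and specificity are conditional on CT status. A model that pools both groups estimates something else: a prevalence-weighted mixture of the two (item 4), or the overall rate of positive device readings (item 11).

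Two kinds of misreading follow. A factor that lowers sensitivity can look much weaker than it is, because CT-positive patients are a small part of the sample. And in item 11, a factor that merely predicts having a hematoma can look like an influence on the device. For an optical device, skin, hair and scalp effects are results that readers will want to interpret. Age is named in the objective, and no other planned analysis covers it.

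**Working it through.** **Inputs from the documents.** 500 patients and 581 measurements (SAP, Study Population); prevalence 0.13 (Protocol 13c, Administrative Summary); sensitivity 0.88 and specificity 0.91 (SAP, Background). The last two belong to the earlier device, and the first of them is "high sensitivity (88%) in detecting hematomas > 3.5cc in volume", not for hematomas of any size. **Assumed:** all factor effects below, and sensitivities of 0.75 and 0.60 as lower values.

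**The plan's own figures.** No figure is given for either regression. The sample-size figures reproduce: 68/0.13 = 523; 523 − 68 = 455; 90% half-widths at p = 0.5 are 0.0997 (n = 68) and 0.0386 (n = 455), against 0.099 and 0.038 stated. At 500 patients, 0.13 × 500 = 65 are CT-positive and 435 CT-negative.

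**What each pooled model sees**, with prevalence p:

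- Item 4: P(correct) = p·Se + (1 − p)·Sp. At the base values, 0.13 × 0.88 + 0.87 × 0.91 = 0.9061.
- Item 11: P(positive) = p·Se + (1 − p)(1 − Sp). At the base values, 0.13 × 0.88 + 0.87 × 0.09 = 0.1927.
- Expected errors: 65 × 0.12 = 7.8 misses and 435 × 0.09 = 39.15 false positives, so 83% of errors are false positives.

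**Odds ratios for a binary factor, prevalence fixed at 13%.** For example, with Se 0.60, P(correct) = 0.078 + 0.7917 = 0.8697, and (0.8697/0.1303)/(0.9061/0.0939) = 0.69. The true odds ratio is (0.60/0.40)/(0.88/0.12) = 0.20.

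| Assumed change | True OR | Item 4 | Item 11 |
|---|---|---|---|
| Se 0.88 to 0.60 | 0.20 | 0.69 | 0.78 |
| Se 0.88 to 0.75 | 0.41 | 0.83 | 0.89 |
| Sp 0.91 to 0.80 | 0.40 (device negative) | 0.44 | 1.70 (device positive) |
| Sp 0.91 to 0.85 | 0.56 (device negative) | 0.61 | 1.36 (device positive) |
| Se to 0.60 and Sp to 0.95 | 0.20 (Se) | 0.98 | 0.58 |

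**A factor that changes prevalence only** (Se 0.88, Sp 0.91 throughout):

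| Prevalence | P(positive) | Item 11 OR | Item 4 OR |
|---|---|---|---|
| 10 to 16% | 0.1690 to 0.2164 | 1.36 | 0.98 |
| 8 to 18% | 0.1532 to 0.2322 | 1.67 | 0.97 |
| 6 to 20% | 0.1374 to 0.2480 | 2.07 | 0.95 |

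Item 4 is nearly free of this artefact at 0.88/0.91, but less so if sensitivity is lower: at Se 0.70, a shift from 10 to 20% moves P(correct) from 0.889 to 0.868, an odds ratio of 0.82.

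**Does CT status cure it?** In 1,000,000 simulated patients with two further covariates and the fall to 0.60, item 4 gave 0.69 and item 11 gave 0.77. Adding a CT main effect to item 11 still gave 0.68. Adding the factor-by-CT interaction recovered 0.20 in CT-positive and 1.00 in CT-negative patients.

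**What 65 CT-positive patients can support.** Misses are 65 × (1 − Se) = 7.8, 16.25 or 26 at Se 0.88, 0.75 or 0.60. With no true effect, the 95% limits for a binary factor's odds ratio lie a factor of exp{1.96·√[1/(n₁q(1 − q)) + 1/(n₂q(1 − q))]} either way, where q is the sensitivity. This is 4.5, 3.1 or 2.7 with an even split, and 6.5, 4.1 or 3.5 with a 20/80 split. Fisher exact power for the fall to 0.60 is 72% with an even split (33 vs 32) and 56% with 52 vs 13. For the fall to 0.75 it is 24% and 19%. In the pooled models, the fall to 0.60 reaches p < 0.05 in about 25% (item 4) and 19% (item 11) of trials with 250 per level.

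**The case against.** The strongest reply is that a different estimand is not an error. Item 4 uses CT to define a correct reading, so it validly models accuracy, which the protocol's Background and Significance names in its aim to "compare the sensitivity, specificity, accuracy, and precision of the InfraScanner 2000™ against brain CT scans at DUH". Item 11 claims only an association with the device result. Both points stand: harm arises only if the coefficients are read as effects on sensitivity or specificity. But the objective asks about exactly those quantities, and nothing else in the plan supplies them for age.

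Item 11 may also be shorthand for item 4's outcome. If so, the prevalence artefact largely goes away at the base values, and the fault is unclear wording. That cannot be settled from the text. Alternatively, item 4 may be meant for CT-positive patients only. The SAP does not say so. On that reading specificity goes unmodelled, and up to 26 parameters (age 1, sex 1, skin 4, hair color 7, thickness 4, length 4, scalp 3, effacement 1, shift 1) face about 8 to 26 misses.

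A reader might infer that the models say nothing about either test characteristic. That goes too far: item 4 tracks a specificity-only change closely. A reader might also infer that a large loss of sensitivity would appear neutral. The figures show attenuation (0.69 and 0.78), not neutrality. The 0.98 needs specificity to rise at the same time and applies to item 4 alone, since item 11 then shows 0.58.

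Finally, the scope is narrow. Hematoma type and location already have tables. Age is the only named factor left, and the others enter as further examples of the same kind.

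**Conclusion.** The point holds, for the exploratory objective only. As written, both models pool across CT status. Item 4 measures overall accuracy and is mainly a specificity model, so its weakness lies in sensitivity: a true odds ratio of 0.20 shows as 0.69, and 0.41 as 0.83. Item 11, taken literally, attenuates these further (0.78 and 0.89) and reports prevalence-only factors as associated with the device result (1.36 to 2.07). No planned analysis gives sensitivity or specificity by age, sex, skin, hair or scalp findings.

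The sizes rest on 13% prevalence, on 0.88/0.91 carried over from the earlier device, and on assumed factor effects. The structural point does not depend on them. A reader might infer that the trial's main results are compromised. They are not: the primary and secondary estimates come from the 2x2 tables, not from these regressions.

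**What to change.** 1. Reconcile item 4 and item 11 into one stated outcome, analysis set, unit and covariate list. If item 4 is kept, label it a model of overall accuracy.
2. Add patient-level sensitivity (CT-positive patients) and specificity (CT-negative patients) with confidence intervals by factor. Take one factor at a time with collapsed categories, starting with age, in the format of the existing 2x2 tables. Any regression should be split by CT status, or include CT status and its interaction with the factor; a CT main effect alone is not enough. Use exact or penalized estimates in CT-positive patients.
3. State that item 11 will not be read as an effect on device performance unless CT status is in the model.

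Patient-level CT status should be the one used in the main 2x2 table, so that the subgroup counts add up to it. No separate rule for repeat scans is needed here.

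The cost is SAP wording and minor programming, since the variables are already collected. The price is imprecision. Sensitivity comparisons rest on about 65 patients, with 95% limits for an odds ratio about 2.7- to 6.5-fold either way; the specificity comparisons, on about 435 patients, are tighter (about 1.9-fold with an even split and 2.3-fold with 20/80). The SAP should call these results descriptive and unadjusted for multiplicity, and should not treat a non-significant sensitivity difference as evidence of no effect.
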